To estimate the **change in expression levels after 3±2 days of treatment compared to placebo**, we will use a mixed effects regression model of the form $CoASY_{ijt} = \beta_0 + \beta_{jt}I(group = j)I(time = t \text{ and } t > 0) + \alpha I(cPKAN) + b_i$, $j = \text{placebo, low, mid, high}$; $t = 1$. Each individual contributes two observations (baseline and after); b_i represents the random intercept for subject. Baseline, represented by β_0 , is constrained to be the same for all groups because of randomization. Our primary approach will treat time as binary (0=baseline, 1=treated), though this can later be expanded to capture differences between days 1-5 of treatment and include more time points. The β_{jt} represent mean changes from baseline for the three dose groups and placebo. An indicator for PKAN type (cPKAN or aPKAN) is included to reflect its role in stratified randomization. We will review regression coefficients as estimates of the magnitude of effect and $\beta_{\text{placebo}1} - (\beta_{\text{low}1} + \beta_{\text{mid}1} + \beta_{\text{high}1})/3 = 0$ with a two-sided alpha of 0.1 to determine whether CoASY mRNA expression levels rose in all the study product-treated participants after initiation of treatment compared to placebo.

Similarly, we will check for **treatment response when the placebo group initiates treatment after month 6** by recoding their observations to use months 6 as 0

(baseline). We will use the same regression model but expect $\beta_{\text{placebo}1}$ to differ from zero. Further, because PKAN types may differ in response, we will test for an **interaction effect between PKAN type and treatment** averaged over dose levels as $CoASY_{ijt} = \beta_0 + \beta_1 I(\text{aPKAN type}) + \beta_2 I(\text{time} = \text{post}) + \beta_{12} I(\text{aPKAN})I(\text{post}) + b_i$, where indicator variables represent active vs placebo, aPKAN vs classic, and β_{12} is the coefficient for their interaction. 50% of participants are expected to have aPKAN.

At six months, we expect CoASY mRNA expression levels to have decreased somewhat, and that **the group with the highest dose will show the lowest expression**. In addition to repeating the comparisons outlined for initiation of treatment above, we will test $\beta_{\text{low}1} > \beta_{\text{mid}1} > \beta_{\text{high}1} > \beta_{\text{placebo}1}$.

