This will be a single site, phase 2, safety and tolerability trial of 4'-phosphopantetheine (4'-PPT), a downstream product of intermediary metabolism in children and adults with PKAN, a inborn error of vitamin B5 metabolism. An initial 6-month, dose-ranging, parallel-group, randomized, double-blind, placebo-controlled phase will be followed by an 18-month, single-dose, open-label phase. There will be up to 2 months for screening and up to 2 months for follow up for up to a total of 28 months participation for this Primary Cohort. During the double-blind phase, participants in the Primary Cohort will be assigned randomly to one of three dose groups or placebo, with a 1:1:1:1 distribution. Once we meet our enrollment target for the Primary Cohort, we will shift additional enrollment directly into a single-dose open-label arm that will last up to 18 months per participant including up to 2 months for screening and up to 2 months for follow up. Our primary hypothesis is that there will be no clinically significant difference in safety or tolerability profiles between active and placebo groups during six months of double-blind parallel-group study, nor between dose groups over up to 18 months of treatment with 4'-PPT. Safety measures will include treatment-emergent adverse events collected at 10 time points and abnormalities on standard laboratory tests collected at 9 time points over 25 months (including follow up) for Primary Cohort participants. For the Open-label Cohort, treatment-emergent adverse events will be collected at up to 7 time points and safety labs at up to 6 time points over up to 20 months (including follow up). Participants will be stratified by PKAN type: classic or atypical, to ensure approximately equal distribution in each arm.

As a secondary, “proof of concept” aim, we will assess the pharmacodynamic profile of CoASY mRNA expression in the peripheral blood of participants receiving 4'-PPT or placebo. We will measure CoASY mRNA expression at 8 time points for the Primary Cohort and at up to 6 timepoints for the Open-label Cohort to examine four secondary hypotheses:

- a. **CoASY mRNA expression levels will rise in all 4'-PPT-treated participants after 1 month of treatment** compared with placebo-treated participants.

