Because PKAN is an ultra-rare disease, we are limited to 64 participants (15 in each arm + 4 potential dropouts allowing for 5% loss to follow-up) whom we will recruit from our established research registry, (prioritizing those participating in our "PKANready" ongoing natural history study) as well as by methods described within the protocol. This will be designated the "Primary Cohort". When our double-blind enrollment goal is met, enrollment of up to 86 additional participants will shift to an open-label arm; this will be designated the "Open-label Cohort". Enrollment into this cohort will be rolling, and thus the duration of follow up will vary based on the point of entry in the overall life of the

study. Our primary objective is to estimate effects of the study product and we will prioritize effect sizes over statistical power in interpreting results. Still, we wish to include sufficient numbers to estimate effects in our secondary and exploratory analyses of CoASY mRNA expression levels with some precision. In preliminary cross-sectional data, we found that the mean CoASY delta Ct (dCt) measures were 1.4 standard deviations higher in classic PKAN children (n=8) than age-matched healthy controls (n=6) on the \log_2 scale, where higher dCt indicates lower CoASY activity (mean=17.39 vs 16.85, SD=0.39). We anticipate that participants at all three dose levels will resemble healthy controls after 3 ± 2 days, while the placebo group will show no change. We simulated this change from baseline for 12 participants per group. For the standard deviation, we performed one set of simulations using the upper limit of the 60% CI for the standard deviation (0.34-0.48) as a conservative estimate. We regressed the dCt value on four indicator variables for study arm after treatment, with the intercept representing the common mean baseline value, and included a random intercept to induce correlation between paired measurements. We then used a Wald test for $\beta_{\text{placebo1}} - (\beta_{\text{low1}} + \beta_{\text{mid1}} + \beta_{\text{high1}})/3 = 0$ at $\alpha=0.05$. Pooling over 1000 simulated datasets, we find that we reject the null in 85-95% of simulations, approximating power to detect this difference at one month between the active and placebo groups.

b. Statistical plan for primary and secondary aims

Safety Analysis

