Similarly, we will check for **treatment response when the placebo group initiates treatment after month 6** by recoding their observations to use month 6 as 0 (baseline). We will use the same regression model but expect $\beta_{\text{placebo}1}$ to differ from zero. Further, because PKAN types may differ in response, we will test for an **interaction effect between PKAN type and treatment** averaged over dose levels as $CoASY_{ijt} = \beta_0 + \beta_1 I(aPKAN \text{ type}) + \beta_2 I(time = post) + \beta_{12} I(aPKAN)I(post) + b_i$, where indicator variables represent active vs placebo, atypical PKAN vs classic, and β_{12} is the coefficient for their interaction. 50% of participants are expected to have aPKAN.

At six months, we expect CoASY mRNA expression levels to have decreased somewhat, and that the group with the highest dose will show the lowest expression. In addition to repeating the comparisons outlined for initiation of treatment above, we will test $\beta_{\text{low}1} > \beta_{\text{mid}1} > \beta_{\text{high}1} > \beta_{\text{placebo}1}$.

As a final step, we will develop a longitudinal model to characterize CoASY mRNA expression profiles over the entire 24-month study period. We plan to use a mixed effects model with random intercept and slope to account for correlation between measurements and to allow individuals to vary from the group mean. We will explore a number of possible parameterizations of the time effect, including fractional polynomials and splines. We will allow for different trajectories by (a) dose group and (b) PKAN type in separate models with a group x time interaction. This model will take the general form $CoASY_{ij} = \beta_0 + \beta_1 t_{ij} + \beta'_2 group + \beta_3 t_{ij} \times group + b_{1i} + b_{2i} t_{ij}$, where t_{ij} represents time on treatment in months (including partial months as decimals) and group indicates dose group or PKAN type, depending on the model.

c. Statistical plan for exploratory aim

Sample Size and Statistical Power Issues

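### The equation for the PKAN type by treatment interaction in CoASY has no active-vs-placebo term, and the coding of post for placebo and the arms fitted are not stated, so what β12 estimates is undetermined

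*Combined protocol and SAP*

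**What the plan says.** Both the protocol (section 10.b, Analysis of secondary endpoints) and the synopsis (Statistical Methods, same subheading) say that PKAN types may differ in response and that an interaction of type with treatment, averaged over dose levels, will be tested.

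- **Equation.** Besides the intercept and the aPKAN main effect, the protocol prints "\beta_2 I(time = post) + \beta_{12} I(aPKAN)I(post) + b_i". The synopsis ends its equation the same way: "\beta_{12} I(\text{aPKAN})I(\text{post}) + b_i".
- **Legend.** The protocol has "where indicator variables represent active vs placebo, atypical PKAN vs classic, and" then β12, which "is the coefficient for their interaction". The synopsis has "where indicator variables represent active vs placebo, aPKAN vs classic, and" and the same definition of β12.

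Three nearby statements bear on the reading:

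- The main CoASY model, just before, covers placebo and all three doses, and gives placebo its own coefficient at the first post-baseline time. The same paragraph describes time as zero at baseline and one when treated.
- The sentence directly before the interaction model re-baselines the placebo group at month 6, when it starts product.
- Section 5 assigns participants to "one of three dose groups or placebo, with a 1:1:1:1 distribution". Section 10.a expects treated participants to resemble healthy controls at about day 3 "while the placebo group will show no change".

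**The concern.** Equation and legend do not match. The legend names an arm indicator that the equation lacks, and the equation uses a time indicator that the legend omits. The terms and subscripts agree in both places, so damage from PDF conversion is an unlikely explanation.

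An interaction of type with treatment asks whether the active-minus-placebo difference in change is the same in atypical and classic disease. A coefficient on aPKAN × post asks whether the two types change by different amounts in whatever data are fitted. These are the same only under conditions that the plan does not state. Two analysts following the text in good faith could report estimates that differ by a quarter.

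The estimate matters here as well as the test. The synopsis reads p < 0.1 together with magnitude and precision, and section 10.a puts effect sizes ahead of power.

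**Working it through.** The plan gives no effect, sample size or power for this interaction, so there is no figure to reproduce. The 85–95% in section 10.a concerns the overall active-vs-placebo contrast.

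**Notation.** D is the type by treatment interaction: the type difference in change on active minus the type difference in change on placebo. c is the type difference in change on placebo. The type difference in change is therefore c on placebo and c + D on active.

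**Reading 1: all four arms, placebo's follow-up coded post = 1.** With complete pairs, β12 is the mean change in atypical minus the mean change in classic participants, pooled over arms. A fitted random-intercept model reproduced this exactly. Three of four arms are active, so with types balanced across arms:

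β12 = 0.75(c + D) + 0.25c = c + 0.75D

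With c = 0:

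- D = 0.27 gives 0.75 × 0.27 = 0.2025.
- D = 0.54 gives 0.75 × 0.54 = 0.405.

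The factor does not depend on SD, correlation or main effect. It does need balance. Fifteen per arm forces a 7/8 split of types. With 22 of 30 atypical and 23 of 30 classic participants on active, a main effect of 0.54 shifts β12 by 0.54 × (23/30 − 22/30) = 0.018.

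**Reading 2: all four arms, post = 1 only for observations on active product.** Placebo's follow-up then counts as a second untreated observation. Generalised least squares gives β12 = D when c = 0. With D = 0 and a hypothetical c = 0.2, β12 is about 0.17 to 0.19 over correlations 0.3 to 0.7, so most of any placebo difference is read as treatment response.

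**Reading 3: on-product data only** (active arms alone, or with placebo re-baselined at month 6). β12 = c + D, provided c also describes the change that would have occurred without product. There is no attenuation, but no comparator either, so all of c is included.

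**Precision at the planned 15 per arm.** Inputs are SD 0.39 and 0.48 (section 10.a), an assumed correlation ρ = 0.5 (none is given), and 8 + 7 placebo and 22 + 23 active participants by type. For the three-way term with a common baseline across arms:

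SE² = SD²(1 − ρ²)(1/8 + 1/22 + 1/7 + 1/23) = SD² × 0.75 × 0.3568

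- SD 0.39: SE = 0.202; 90% half-width 1.645 × 0.202 = 0.33.
- SD 0.48: SE = 0.248; 90% half-width 1.645 × 0.248 = 0.41.

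The half-width scales with √(1 − ρ²), so ρ from 0.3 to 0.7 gives about 0.27 to 0.45 over the two SDs. Under Reading 2 the half-width at ρ = 0.5 is about 0.18 to 0.23.

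**The case against.** The strongest reply is that the intent is stated in words and that the printed equation can be made to serve it. The plan's own time coding is one when treated. If post marks only observations on active product, β2 is treated versus untreated, β12 is type by treatment, and the legend fits. That version loses nothing to attenuation when placebo is stable, which is what section 10.a expects at day 3, and it is considerably more precise than the three-way term. It is a defensible choice.

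This stands as a possible reading and as an acceptable repair. It does not remove the problem, because the text never says it and the neighbouring model gives placebo a post-baseline coefficient of its own. The on-product reading is also possible, but then an active-vs-placebo legend does not apply.

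A reader might infer that the test will produce false positives by reporting drift as differential response. The documents do not support that. They give no figure for a type difference in change on placebo, and they expect no placebo change at day 3. Without drift, Reading 1 does not reject too often: in simulation at 15 per arm (main effect 0.54, correlation 0.5), it rejects in about 6 to 7% of trials with no interaction, at a nominal 10%. The drift harm is conditional.

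Nor can one say that the planned analysis is definitely type by time. That holds under Reading 1 only.

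**Conclusion.** The point holds as a specification gap. The equation does not match its legend or stated purpose, and the choices that decide what β12 means are missing. If all four arms are fitted with placebo's follow-up coded as post, the stated quantity is understated by 25%, given 1:1:1:1 allocation, types balanced across arms in the Per-Protocol set, and no type-specific change on placebo. Under the other two readings β12 equals the interaction when placebo does not change, and absorbs most or all of any placebo difference between types when it does.

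Severity is low. CoASY is described as an exploratory, proof-of-concept biomarker, and this is a sub-analysis of it. A reader might go on to doubt the main CoASY contrast or the safety conclusions. Neither is touched: the main contrast has explicit terms for each arm, and the primary safety and tolerability analyses do not use this model.

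**What to change.** In both section 10.b and the synopsis, do one of the following.

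1. **Match the equation to the purpose.** Add post × active (pooled over doses) and post × aPKAN × active to the printed terms, keep the baseline common across arms, define the three-way coefficient as the type by treatment interaction, and report it with a 90% CI. An equivalent parameterisation is fine.
2. **Keep the short equation.** Define post as on active product only, or restrict the model to on-product data. State the assumption that placebo does not change, and correct the legend where it no longer applies.

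In either case, say whether the repetition of the comparisons at month 6 includes this model; the present wording leaves that open.

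The cost is wording only. Option 1 is imprecise because 7 or 8 placebo participants per type anchor it: its half-width of 0.33 to 0.41 is wider than an interaction of 0.27, so it should be read as an estimate. Option 2 is tighter but cannot separate placebo change from response.

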Graphic displays may be provided to illustrate the results over time. Initial review of group differences and determination of clinical significance will be performed by an unaffiliated physician familiar with the study population and blinded to treatment arm.

Tolerability Analysis

We will compare the number of participants retained in each arm at each of the follow-up time points [0-(0+3 days)-1-3-6-(6M+3 days)-7-9-12-18-24-25 months for the Primary Cohort; and 0-(0+3 days)-1-3-6-9-12-18-19 for the Open-label Cohort], taking into account whether dropout seems plausibly related to study participation and the mean percent of study product consumed. High retention in the study and product consumption per-protocol will be considered evidence of tolerability.

Other analyses

Analysis of secondary endpoints

We will estimate a CoASY pharmacodynamic profile in response to different doses of the study product in the Per-Protocol dataset. CoASY mRNA expression levels are continuous, measured in normalized differences in cycle times (ΔCt) on the \log_2 scale. Lower ΔCt indicates higher expression levels. We will use regression models controlling for PKAN type to estimate mean levels by treatment arms, including mixed effects when modeling over multiple time points.

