We will compare the number of participants retained in each arm at each of the follow-up time points [0-(0+1week)-1-3-6-(6M+1week)-7-9-12-18-24-25 months for the Primary Cohort; and 0-(0+1week) -1-3-6-9-12-18-19 for the Open-label Cohort], taking into account whether dropout seems plausibly related to study participation and the mean percent of study product consumed. High retention in the study and product consumption per-protocol will be considered evidence of tolerability.

Analysis of secondary endpoints

We will estimate a CoASY pharmacodynamic profile in response to different doses of the study product in the Per-Protocol dataset. CoASY mRNA expression levels are continuous, measured in normalized differences in cycle times (ΔCt) on the \log_2 scale. Lower ΔCt indicates higher expression levels. We will use regression models controlling for PKAN type to estimate mean levels by treatment arms, including mixed effects when modeling over multiple time points.

To estimate the **change in expression levels after 3±2 days of treatment compared to placebo**, we will use a mixed effects regression model of the form $CoASY_{ijt} = \beta_0 + \beta_{jt}I(group = j)I(time = t \text{ and } t > 0) + \alpha I(cPKAN) + b_i$, $j = \text{placebo, low, mid, high}$; $t = 1$. Each individual contributes two observations (baseline and after); b_i represents the random intercept for subject. Baseline, represented by β_0 , is constrained to be the same for all groups because of randomization. Our primary approach will treat time as binary (0=baseline, 1=treated), though this can later be expanded to capture differences between days 1-5 of treatment. The β_{jt} represent mean changes from baseline for the three dose groups and placebo. An indicator for PKAN type (cPKAN or aPKAN) is included to reflect its role in stratified randomization. We will review regression coefficients as estimates of the magnitude of effect and test $\beta_{\text{placebo}1} - (\beta_{\text{low}1} + \beta_{\text{mid}1} + \beta_{\text{high}1})/3 = 0$ with a two-sided alpha of 0.1 to determine whether CoASY mRNA expression levels rose in all the study product-treated participants after initiation of treatment compared to placebo.

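### The six-month ordered test of CoASY runs the wrong way for the three active doses: on the delta-Ct scale it says expression rises with dose

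*Combined protocol and SAP*

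**What the plan says.** The synopsis (Analysis of secondary endpoints) and protocol section 10.b give the same plan for CoASY mRNA.

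- **Scale.** The outcome is delta-Ct on the log2 scale, and a lower value "indicates higher expression levels. We will use regression models controlling for PKAN type". Section 10.a agrees: higher dCt means lower CoASY activity, with a mean of 17.39 in classic PKAN and 16.85 in healthy controls.
- **Coefficients.** The β's "represent mean changes from baseline for the three dose groups and placebo", with one common baseline for all arms. The power simulation used the same outcome without a sign change: "We regressed the dCt value on four indicator variables for study arm after treatment".
- **Six-month expectation.** In words, "we expect CoASY mRNA expression levels to have decreased somewhat", "and that the group with the highest dose will show the lowest expression". Secondary hypothesis c in section 5 says the same: at six months, expression is inversely related to dose.
- **Six-month test.** The next sentence begins "In addition to repeating the comparisons outlined for initiation of treatment above, we will test" and gives the chain β_low1 > β_mid1 > β_high1 > β_placebo1.

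**The concern.** The sentence in words and the inequality that follows it point in opposite directions on the declared scale. If the highest dose has the lowest expression, it has the highest delta-Ct and therefore the largest β. The chain gives it the smallest β of the three active doses.

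Of the four secondary hypotheses in section 5, c is the only one that predicts a difference between active doses. Section 6 says the dose range is there to test the biomarker hypotheses. If the chain is applied as written, data that bear out hypothesis c would be read as contradicting it, and data showing expression rising with dose would be read as support. If the direction is settled only after the data are seen, the choice is open to the charge that the results drove it.

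**Working it through.** **1. Direction, from the plan's definitions alone**

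Expression moves opposite to delta-Ct, and all arms share one baseline, so a larger β means lower expression.

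- Hypothesis c: expression low > mid > high, which on delta-Ct is β_high1 > β_mid1 > β_low1.
- Chain as written, active part: β_low1 > β_mid1 > β_high1, which means expression high > mid > low.

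Active-dose pairs in the order hypothesis c requires: 0 of 3.

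**2. Sign of the β's, checked on the plan's own figures**

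Section 10.a expects treated participants to resemble healthy controls at day 3 and placebo not to change. The expected active β is 16.85 − 17.39 = −0.54, and the placebo β is 0. The contrast of placebo minus mean active is 0 − (−0.54) = +0.54. A rise in expression is therefore a negative β. The six-month test is introduced as an addition to repeating these comparisons and uses the same symbols.

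**3. Where placebo falls**

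The plan does not say where placebo should lie relative to the active arms at six months. Assume hypothesis c is true and placebo stays at its untreated level. There are two cases:

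| Treated expression at six months | True order on delta-Ct | Chain read on delta-Ct | Chain read on −delta-Ct |
|---|---|---|---|
| Between day-3 and untreated levels (active β between −0.54 and 0) | placebo > high > mid > low | 0 of 6 pairs agree | 6 of 6 agree |
| Below the untreated level (active β above 0) | high > mid > low > placebo | 3 of 6 agree (the placebo pairs only) | 3 of 6 agree (the active pairs only) |

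On delta-Ct, the active pairs are wrong in both cases. Placebo's last place does not show which scale was meant: on delta-Ct it gives placebo the highest expression, and on −delta-Ct the lowest.

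**4. Illustration of size**

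The plan gives no six-month effect, no pre/post correlation ρ and no test statistic for the chain. The quantity below is therefore only the chance that the three estimated active β's fall in a given order.

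With a common baseline mean and a random intercept, differences between arm β's behave like differences of independent normals with variance SD²(1 − ρ²)/n. The two adjacent differences each have twice that variance and correlate at −0.5.

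Worked cell: n = 15 per arm, SD = 0.39, ρ = 0, high-minus-low difference 0.20 in equal steps of 0.10.

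- Variance of each estimate: 0.39²/15 = 0.01014.
- SD of an adjacent difference: √(2 × 0.01014) = 0.142.
- Standardised step: 0.10/0.142 = 0.70.
- P(both adjacent differences in the corrected order) = 0.533. P(both in the written order) = 0.016.
- A check with 20,000 simulated trials gave 0.535 and 0.016.

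The ranges below cover n = 12 (the simulated size) and 15 (the planned size), SD 0.39 and 0.48 (section 10.a), ρ = 0 and 0.5 (assumed), and steps that are equal or proportional to dose (5, 15, 20 mg/m²):

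| Assumed high − low, delta-Ct, under hypothesis c | Written order | Corrected order |
|---|---|---|
| 0 | 16.7% | 16.7% |
| 0.10 | 5–8% | 28–37% |
| 0.20 | 1–3.5% | 42–59% |
| 0.30 | 0.1–1.2% | 55–78% |

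If expression instead rises with dose by the same amounts, the two columns swap.

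**The case against.** The strongest reply is that the authors were thinking in terms of expression. The endpoint is called expression throughout, the model's outcome symbol is CoASY rather than delta-Ct, and the direction is stated correctly in words just before the chain. Read on the expression scale, low > mid > high is exactly hypothesis c. That may well be what was meant. But the text does not say so, and it conflicts with the declared outcome, with the quantity regressed in section 10.a and with the reuse of the same β's. It points to one of the two repairs; it does not make the current text consistent.

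Several points on reach do stand:

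- A two-sided p-value would not change; only its reading against the chain would.
- The plan calls a p-value below 0.1 significant only if the size and precision of the effect support it. It also fits a dose-group-by-time model and plots individual profiles, none of which depends on the chain.
- Hypothesis c is missing from the hypothesis lists in the synopsis and section 2–3.
- The order probabilities rest on assumed effects and correlations and are not the error rates of any test in the plan. At ρ = 0.8 the worked cell becomes about 76% corrected and 0.15% written, outside the tabulated range. The sign error needs none of these figures.
- The plan gives no statistic, sidedness or alpha for the chain. That is a separate gap, and correcting the direction does not close it.

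**Conclusion.** The concern holds. On the scale the plan declares, the six-month inequality reverses all three active-dose pairs relative to hypothesis c and to the sentence directly before it. This follows from the documents' definitions without outside assumptions. The whole-chain count (0 of 6 pairs) also requires treated expression to lie between its day-3 and untreated levels, with placebo unchanged. The percentages depend further on the assumed effects and correlations.

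It should be fixed, because a directional test followed literally would yield the opposite conclusion. The damage is confined to one secondary, proof-of-concept biomarker claim. The primary safety and tolerability conclusions, the two-sided day-3 contrast and the sample size are unaffected.

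**What to change.** In both the synopsis (Analysis of secondary endpoints) and section 10.b, before the six-month data are analysed, do one of the following:

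1. Write the active-dose order on delta-Ct as β_high1 > β_mid1 > β_low1.
2. Keep low > mid > high and state that, for this test, the β's are on the expression scale (−delta-Ct).

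Under either option, state where placebo is expected to lie on the chosen scale, since its current last place means opposite things on the two. It would be sensible to name the test statistic and its sidedness in the same edit.

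The cost is a one-line correction in two places. No data, visits or sample size are involved.
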